It may be useful to include a brief synopsis of the study for quick reference. Complete information and, if required, add additional rows.

Study Title	Virtual Reality for Pain and Anxiety in Children
Internal ref. no. (or short title)	B00823
Study Design	Feasibility/Acceptability study
Study Participants	Children aged 5-13 years who require cannulation or venepuncture as an inpatient
Planned Size of Sample (if applicable)	32
Follow up duration (if applicable)	None
Planned Study Period	4 weeks
Research Question/Aim(s)	
 • Conduct initial acceptability/feasibility testing of VRH use with children undergoing venepuncture or cannulation in an acute, often unplanned inpatient setting in a children's hospital. • Assess level of child and parent reported pain during procedure as well as change in heart rate.

Virtual Reality for Pain and Anxiety in Children

	
 • Generate pilot data to design software and develop methods, outcome measures and patient/family engagement for a large randomised control trial (RCT) in the same setting to establish efficacy of VRH in reduction of perceived pain.
--	--

FUNDING AND SUPPORT IN KIND

FUNDER(S) (Names and contact details of ALL organisations providing funding and/or support in kind for this study)	FINANCIAL AND NON FINANCIAL SUPPORT GIVEN
Manchester University NHS Foundation Trust Contact details as above	£9380
VREvo Contact details as above	Non-financial advice and support given in planning of study and in use of Virtual Reality Headsets.

ROLE OF STUDY SPONSOR AND FUNDER

Manchester Foundation Trust are the main sponsor. They will have joint responsibility with the study team for the design, conduct and management of the study. The study team will perform data interpretation and analysis and then write the manuscript. They will take responsibility for submission of the manuscript for publication dissemination of results. They will take responsibility for the planning of follow up studies. They and not the funder will control all final decisions over the study.

VREvo are a Virtual Reality Education company part owned by the University of Manchester. They were involved in the planning of the study and will aid in the use of the technology during the study. They have provided training on how to use the technology. They will be involved in drafting the final manuscript and planning any follow up studies.

1 BACKGROUND

Virtual reality (VR) technology is making rapid progress into many aspects of daily life and work and the potential applications within the field of medicine are huge, particularly amongst the paediatric population.

Venepuncture and cannulation are common procedures in paediatrics and, despite developments in analgesic sprays and creams, it remains a procedure most children dread and which is uniquely distressing to patients, families and clinicians alike. Even children who undergo regular venepuncture often find this distressing. A lot of the pain and fear associated with venepuncture is psychological and secondary to the fact that most children become apprehensive before and distressed during the process. The sight of doctors, nurses, clinical environments and apparatus required for cannulation/venepuncture is frightening to young children. Distraction is very effective in reducing pain and anxiety in paediatric procedural pain¹ but requires multiple members of skilled staff, cooperative, engaged parents and the time to coordinate all of this.

The immersive nature of wearing a Virtual Reality Headset (VRH) in an outpatient or emergency department setting provides a very effective distraction to children, reducing the anxiety and pain associated with venepuncture and cannulation². A number of studies have explored the application of VRH in children and young people and reported promising early outcomes. However, as these studies are variable in design, software application, setting and cultural context, it is not possible to extrapolate acceptability, satisfaction and positive gain between groups tested for VRH utility. There have been no VRH studies in children in the UK and no studies have evaluated the application in inpatient children with complex disease.

In the University of Manchester, our group has engaged with children to assess feasibility of use and acceptability of different VRHs. VRHs were very well received and the Oculus Go was felt to be an appropriate size and fit for children aged 5 to 13 years. Initial and qualitative feedback has been overwhelmingly positive with 96% of over 300 people surveyed expressing enthusiasm about the use of VRHs.

The majority of venepuncture and cannulation occurs in an inpatient setting and therefore often with minimal prior notice due to staff availability and the transient nature of cannulae in small children. This means that additional staff support for distraction is often not available during the day and almost never out of hours in busy hospitals with a stretched workforce. As children become older they are more aware of the hospital and often become more anxious and less easily distracted by standard play distraction techniques. The use of a VRH could be easily employed at short notice by a single practitioner when venepuncture/cannulation is required and support staff are not available for distraction. Parents can be left to supervise their child using the VRH while clinicians focus on the clinical procedure. No studies have investigated the feasibility and acceptability of VRH use in a paediatric inpatient setting in a busy Children's Hospital where distraction is often required at short notice.

¹Ali, *PediatrEmergCare*, 2016

²Chan, *JPediatr*, 2019

2 RATIONALE

We want to know if it is feasible to use VRH for distraction during painful procedures in paediatric inpatients. Utility of this cannot be extrapolated from outpatient/clinic/emergency department studies.

Virtual Reality for Pain and Anxiety in Children

We want to know if this is acceptable to patients, parents and clinicians and if they would be keen for this to become routine practice for painful procedures in our hospital.

Painful procedures are a source of significant stress and anxiety to children who are inpatients in hospital and it is our duty as clinicians to understand if there is a way in which we can reduce this stress and anxiety.

If use of VRHs during painful procedures was found to be simple, effective and desirable this could be easily and quickly rolled out to all of our inpatient wards and later to other hospitals. This could have a significant impact upon the inpatient stay of children all over the country.

This project will be conducted in accordance with the study protocol and the ethical principles outlined by Good Clinical Practice (GCP) and the Declaration of Helsinki in its most current version.

3 THEORETICAL FRAMEWORK

The above approach is entirely appropriate to answer our research question. As there have been no studies using VRHs for painful procedures in children who are inpatients before, it would be inappropriate to conduct a randomised controlled trial looking in to relative pain and anxiety reduction without first conducting feasibility and acceptability trials. This is why we have chosen the above approach. This study will directly answer our study questions.

4 RESEARCH QUESTION/AIM(S)

4.1 Objectives

1. Conduct initial acceptability/feasibility testing of VRH use with children undergoing venepuncture or cannulation in an acute, often unplanned inpatient setting in a children's hospital.
2. Assess level of child and parent reported pain during procedure as well as change in heart rate.
3. Generate pilot data to design software and develop methods, outcome measures and patient/family engagement for a large randomised control trial (RCT) in the same setting to establish efficacy of VRH in reduction of perceived pain.

4.2 Outcome

1. Perceived and reported pain/anxiety scores for children undergoing venepuncture or cannulation with VRH.
2. Change in heart rate before, during and after painful procedure
3. Clinicians' feedback on the use of VRH in inpatient painful procedures

5 STUDY DESIGN and METHODS of DATA COLLECTION AND DATA ANALYSIS

Practitioners will be encouraged to contact the research team each time they are to perform a procedure between 0830H and 1600H and, unless already with another child using VRH, the research team will come to speak to parents to consent to the study. If consent is obtained then the procedure will be performed using current standard care as well as use of a VRH. The Oculus Go is a cheap and quick to set up headset. Off the shelf software will be selected that will distract but not require the movement of both arms. Software such as The Blu, Ocean Rift and Pet lab will be selected, dependent upon the age of the patient.

VRH will be brought to the room planned for procedure and set up for the child as part of the preparation for venepuncture/cannulation. Prior to application of VRH children will be asked to score their current pain score using the Wong Baker Faces Score (WBFS)¹. This will be transcribed by the researcher. VRH use will be commenced at least 3 minutes prior to commencement of painful procedure. The procedure will then be performed by the practitioner and VRH supervised by parent(s). The researcher will not participate in the procedure beyond initial setup of the VRH to ensure real world feasibility is being tested for. Once the procedure is completed, the child will be allowed to continue using the VRH while clinicians and parents involved in the procedure fill in the feedback forms.

Feedback forms for parents will focus on perceived pain score and short qualitative review regarding acceptability, whether they would consider repeat application at subsequent venepuncture procedures, if VRH was well tolerated and whether they felt it helped. Feedback from clinicians will focus on ease of use of VRH, if they felt it facilitated procedure or whether it was felt to prolong the procedure. Forms will be filled in by parents and clinicians themselves and then handed to the researcher.

Children will then have the VRH removed and be asked to score their current pain again using the WBFS. Children's WBFS will be compared pre and post procedure. Assessment of acceptability/feasibility for children will be based on 3 **questions** – 1. Do they like it, 2. Was VRH wear comfortable and 3. Did they feel unwell whilst wearing VRH. Questionnaire answers will also be used to design future trials and bespoke VR software.

Questionnaires will then be pseudonymised and transcribed on to a secure computer for analysis of data. Interpretation of data will be performed by the clinical research team. Any statistical analysis required will be performed using SPSS Statistics 25 on pseudonymised datasets. Paper questionnaires will be kept in a locked drawer, in a locked room, on a locked research unit where access is only via swipe card. Access to paper questionnaires and digital data will only be for the immediate clinical research team of [name] and [name].

¹ Wong-Baker FACES Foundation (2018). Wong-Baker FACES® Pain Rating Scale. Retrieved [11/10/19] with permission from <http://www.WongBakerFACES.org>

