6 STUDY SETTING

The study will be performed on all paediatric inpatient wards at Royal Manchester Hospital. The research team will be based on the CCRF (Children's Clinical Research Facility) and will move to each ward as required to provide VRH for procedures. Participants will be accessed via identification by clinicians performing painful procedures.

Royal Manchester Children's Hospital is the busiest children's hospital in the UK. Venepuncture and cannulation are routinely performed by a wide variety of staff including doctors, nurses and the IV access team. It is therefore an ideal location to conduct this study. Participants will undergo recruitment, discussion with the research team, consent and procedure all in the same location within

Virtual Reality for Pain and Anxiety in Children

Royal Manchester Children's Hospital. Participation in the study will not impact upon patient care and will not require patients or parents to move anywhere or do anything they would not already be doing as part of their inpatient stay.

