8.6 Data protection and patient confidentiality

Only the direct clinical care team will have access to the patients' personal data. The research team (comprising of doctors in the Children's hospital) will not review medical/surgical data for the patient as this is irrelevant to the study and will contravene Data Protection and Confidentiality regulations as per standard clinical practice.

The study data will be analysed by our research fellow at the Royal Manchester Children's Hospital. The results will be discussed with the senior statistician who is also based in the same NHS Trust.

Data will be stored in the department of Paediatric Endocrinology at the Royal Manchester Children's hospital, on a departmental server kept secured by username and passwords. Access to the department is swipe card controlled and the room where the NHS computers with departmental drives are based is secured by a combination lock. Storage of research data will be overseen by the research team. Paper data will be stored in fire proof filing cabinets and kept under lock and key.

Storage and destruction of research data will be carried out in line with trust archiving policies

This is a feasibility and pilot study upon which a formal clinical trial will be launched. While this is an intervention related study, the primary aim is feasibility and applicability rather than efficacy.

The data custodian is the Chief Investigator.

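### Section 5 claims to test real-world feasibility, but a researcher sets up the headset in every enrolled use and the listed outcomes include no objective feasibility measure

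*Protocol*

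**What the plan says.** All references are to the protocol.

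- **Motivation (Section 1).** The headset is put forward for inpatient wards, where support staff are often not free. It "could be easily employed at short notice by a single practitioner", with the parent supervising it while the clinician does the procedure.
- **Primary aim (Section 8.6).** The protocol states that "the primary aim is feasibility and applicability rather than efficacy".
- **Who does what (Sections 5 and 6).** The research team "will move to each ward as required to provide VRH for procedures". Section 5 then says: "The researcher will not participate in the procedure beyond initial setup of the VRH to ensure real world feasibility is being tested for". Practitioners call the team "between 0830H and 1600H and, unless already with another child using VRH, the research team will come to speak to parents".
- **What is collected (Sections 4.2 and 5).** The listed outcomes are pain/anxiety scores, change in heart rate and clinicians' feedback. "Feedback from clinicians will focus on ease of use of VRH", and on whether the headset helped or prolonged the procedure. Parents report on tolerability, perceived help and willingness to repeat. "Assessment of acceptability/feasibility for children will be based on 3" questions: liking, comfort and feeling unwell.
- **Early removal (Section 8.1).** The protocol foresees that a child may not keep the headset on, and says it is then removed and not re-applied.

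**The concern.** For a device meant to be used at short notice without helpers, set-up is a critical step. The study gives that step to a researcher, yet describes the arrangement as a test of real-world feasibility. Clinicians then rate the ease of use of equipment that somebody else prepared.

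Section 2 says that if headset use proves simple, effective and desirable, it could be rolled out quickly to all inpatient wards. Clinician-rated ease of use is the item most likely to be read as evidence of simplicity, and here it would describe a supported setting. Objective 3 also asks for pilot data to develop methods for a randomised trial. As the outcomes are listed, that trial would inherit no figure for how long set-up takes or how often the headset stays on.

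**Working it through.** **1. The plan's own figure.** Section 7.2.1 gives a 95% Clopper-Pearson interval for 75% acceptability in 32 children, that is 24/32:

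- lower limit = Beta(0.025; 24, 9) = 56.6%
- upper limit = Beta(0.975; 25, 8) = 88.5%

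This reproduces the stated 56.6-88.5%. The figure concerns acceptability to the child and is not affected by this point.

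**2. Intended use against observed use.**

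| Step | Intended use (Section 1) | Study (Sections 5 and 6) | Intended use observed? |
|---|---|---|---|
| Headset supplied | Practitioner, short notice | Research team comes to the ward | No |
| Set-up | Practitioner, no support staff | Researcher | No |
| Procedure | Practitioner | Practitioner | Yes |
| Supervision of headset | Parent | Parent | Yes |
| Timing | Short notice, day and out of hours | Unplanned calls, 0830H to 1600H, if the team is free | In part |

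Section 5 is in the passive voice about who brings the headset to the room. That the research team does so is taken from Section 6.

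**3. Size of the gap.** With researcher set-up in all 32 planned uses, observations of set-up without a researcher number 32 − 32 = 0. Sample size cannot make up for this. If all 32 clinician ratings were favourable, the exact lower limit would be 0.025^(1/32) = 0.891, giving an interval of 89.1-100%. That interval would look convincing, but it would describe researcher-supported use only. The 32/32 result is hypothetical and no protocol figure depends on it.

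**4. What is measured on feasibility.**

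| Quantity | Collected as opinion | Listed as an objective outcome |
|---|---|---|
| Ease of use | Yes, clinician | No |
| Procedure prolonged | Yes, clinician | No |
| Tolerability | Yes, parent and child | No |
| Set-up time | No | No |
| Headset on to the end, or removed early | No | No |
| Researcher help after set-up | No | No |

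**5. What a retention count would give.** If the headset stayed on in 28/32 uses, the exact 95% interval would be 71.0-96.5%. If it stayed on in 30/32, it would be 79.2-99.2%. These counts are illustrative. They show that 32 uses give a usable figure once the item is recorded.

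**6. Whether it can be recovered later.** Section 8.8 says families cannot be contacted after data collection, and Section 8.6 says the research team will not review medical data. Anything not written down at the bedside is lost.

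**The case against.** The strongest reply is that unsupported set-up is never promised. The single practitioner appears only in Section 1, as something a headset could allow. Objective 1 speaks of initial acceptability and feasibility testing in an acute inpatient setting. The sentence in Section 5 openly states that the researcher does the set-up, so its real-world claim can be read as covering only what follows. For a first study, researcher set-up is reasonable. The questionnaires are not shown and may hold more items than Section 5 summarises.

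Much of this stands. Researcher set-up is a defensible choice and need not change, and it is not concealed. What remains is that the claim is worded more broadly than the observed part of the process, and that Section 4.2 fixes outcomes without an objective feasibility measure. What is collected at the bedside cannot be left to a later analysis plan.

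A reader might also infer several stronger points that the protocol does not support:

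- **That nothing about set-up or completion is measured.** Opinions on ease, prolongation and tolerability are collected. They are subjective and indirect.
- **That short-notice use is never seen.** Practitioners call as procedures arise, so unplanned procedures are partly observed.
- **That parent supervision departs from the intended use.** Section 1 describes exactly that.
- **That the child questions are irrelevant to feasibility.** Comfort and feeling unwell bear on whether a child can wear the headset.
- **That each use adds at least 3 minutes.** Section 5 places headset set-up within the preparation for the procedure, so the 3-minute lead-in may overlap time that would be spent anyway.

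**Conclusion.** The point holds in a limited form. The design can show whether a practitioner and parent manage the procedure once a researcher has supplied and set up the headset. It cannot show that ward staff can set it up themselves: 0 of 32 planned uses bear on that. Ease-of-use ratings carry the same limit. Separately, the primary aim of feasibility rests on opinion alone among the listed outcomes, even though the protocol foresees early removal.

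This assumes that researcher set-up applies to every enrolled use, as Sections 5 and 6 describe, and that the unseen forms do not already record times and retention. If they do, the second part reduces to listing those items in Section 4.2. The wording point stands either way. No stated figure changes. The matter should be put right before recruitment but does not undermine the study.

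**What to change.** Keep researcher set-up, and make three changes.

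1. **Log.** The researcher already present records time of call, arrival, headset on, procedure start and procedure end, whether the headset stayed on to the end, and any help given after set-up. Arrival to headset-on also contains the information sheet, consent and the baseline pain score, so one further entry for the start of set-up is needed to isolate set-up time.
2. **Section 4.2.** List set-up time, headset kept on to the end, early removals and researcher help after set-up as feasibility outcomes, with exact intervals for the proportions.
3. **Section 5.** State that the feasibility and ease-of-use results apply to use with researcher set-up, and that feasibility for a single practitioner without support will not be concluded from this study.

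The cost is one short log sheet per procedure, a few lines of text and a narrower feasibility claim. Sample size and care are unchanged. The logged set-up time will be a researcher's time and should be reported as such, since a ward practitioner's may differ.

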8 ETHICAL AND REGULATORY CONSIDERATIONS

8.1 Assessment and management of risk

Some children may not prefer to keep the Virtual Reality Headsets over their faces. They may also feel dizzy and be sick. If so, the headsets will be immediately removed and not re-applied. The child will continue to have the routine procedure without application of VRH.

If parents or children are uncomfortable with the application of technology, they will not be consented and VRH will not be applied.

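### Dizziness or sickness that starts when the headset comes off, or afterwards, is recorded by neither the parent form nor the child's question

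*Protocol*

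**What the plan says.** Section 5 of the Protocol sets out the order of events. When the procedure ends, "the child will be allowed to continue using the VRH while clinicians and parents involved in the procedure fill in the feedback forms". The parent form covers the perceived pain score, acceptability, willingness to use the headset at a later procedure, and "if VRH was well tolerated and whether they felt it helped". Completed forms go to the researcher.

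The next step is on the child's side: "Children will then have the VRH removed and be asked to score their current pain again using the WBFS". The text then continues "Assessment of acceptability/feasibility for children will be based on 3" questions: liking, comfort, and "Did they feel unwell whilst wearing VRH".

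Three other places bear on the point:

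- Section 8.1 says of the children: "They may also feel dizzy and be sick". If this happens, or the child does not want the headset on, it comes off at once and stays off.
- The synopsis gives follow-up as none.
- Section 8.8 says the research team has no means of reaching families once the data are collected.

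**The concern.** The two sources on tolerability stop at or before the same moment. The parent may judge tolerance and repeat use while exposure is still running, before seeing the child without the headset. The child is asked about the period of wear and nothing later. Symptoms that begin as the headset comes off, or in the minutes after, fall outside both.

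These are the harms the Protocol itself expects. Section 8.1 names them, and Section 7.1.2 keeps out children known to have had them with earlier headset use.

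The answers will be used. Section 2 asks whether the headset is acceptable to patients, parents and clinicians, and Section 5 says the questionnaires will inform future trials and software. Because there is no later contact, what is not asked at the bedside cannot be recovered.

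**Working it through.** **Step 1. What each source covers, as Section 5 describes it.**

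| Period | Parent tolerance and repeat-use items | Child's third question |
|---|---|---|
| Wear during the procedure | Covered | Covered |
| Continued wear after the procedure | Not fully covered if the child keeps the headset on while the form is filled in | Covered |
| Removal and the minutes after | Not covered where the form is completed before removal | Not covered (wear only) |
| Later | Not covered | Not covered; no follow-up, no contact |

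The second row is a gap in the parent form only. From removal onwards, the gap is common to both sources.

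**Step 2. Reproduce the Protocol's figure.** Section 7.2.1 gives n = 32 and a 75% acceptability target with a 95% Clopper-Pearson interval of 56.6 to 88.5%. For x events in n, the lower limit is the 0.025 quantile of Beta(x, n − x + 1) and the upper limit is the 0.975 quantile of Beta(x + 1, n − x). With x = 24, n = 32:

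- lower: Beta(24, 9) at 0.025 = 56.6%
- upper: Beta(25, 8) at 0.975 = 88.5%

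The figure reproduces. Nothing in this point disputes it.

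**Step 3. Weight of one missed child.** 1/32 = 3.1 percentage points.

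**Step 4. Illustration for the acceptability proportion.** Assumption, not in the Protocol: each missed symptom would have turned an acceptable rating into a not acceptable one.

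| Missed children | Proportion | Exact 95% interval |
|---|---|---|
| 0 | 24/32 = 75.0% | 56.6 to 88.5% |
| 1 | 23/32 = 71.9% | 53.3 to 86.3% |
| 2 | 22/32 = 68.8% | 50.0 to 83.9% |
| 3 | 21/32 = 65.6% | 46.8 to 81.4% |

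**Step 5. How many might be missed.** The Protocol gives no rate of symptoms that start only after removal. For an assumed rate p, the expected number missed is 32p and the chance of missing at least one is 1 − (1 − p)^32.

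| Assumed p | Expected missed | Chance of at least one |
|---|---|---|
| 2% | 0.6 | 47.6% |
| 5% | 1.6 | 80.6% |
| 10% | 3.2 | 96.6% |
| 15% | 4.8 | 99.4% |

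**Step 6. Illustration for a symptom count.** With 0/32 recorded, the exact 95% upper limit is 1 − 0.025^(1/32) = 10.9%. With 2/32 it is 6.25% (0.8 to 20.8%). The intervals overlap widely, but a report of no events and a report of two read differently.

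Steps 4 to 6 show scale only. They do not estimate a bias.

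**The case against.** The strongest case against runs as follows.

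- **Late wear is covered.** The child's question is described after removal and spans the whole period of wear, including continued use after the procedure. This stands. A reader might infer that symptoms late in use are lost; the text does not support that. Only the parent form can miss them.
- **Not every parent form precedes removal.** Continued use is offered, not required, and under Section 8.1 the headset is already off a child who felt ill. Parents supervise the headset, so they would see this. This stands: the parent-form gap applies only where the child keeps the headset on.
- **The parent form does not decide child acceptability.** Section 5 rests that on the child's three questions, and Section 7.2.1 sizes the study on patient acceptability. This stands for the 75% target. It does not dispose of the point, because parent acceptability is a question of its own in Section 2 and the child's third question has the post-removal gap itself.
- **Direction.** The parent item is a global judgement and could move either way with longer observation. This stands for that item. For a record of whether symptoms occurred, stopping early can leave events out but cannot add any.
- **The forms are not shown.** Section 5 summarises them, so the actual wording might be wider. This is a fair caution. As summarised, however, the child's item is expressly confined to wear.
- **Rating promptly while the child is occupied is reasonable.** This is so for the pain score and for whether the headset helped. It is a weaker argument for tolerance, which is not complete until exposure ends.

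**Conclusion.** The point holds in a narrow form. By the stated order and wording, dizziness or sickness starting at or after removal is captured by neither source and cannot be recovered later. In addition, where the child keeps the headset on, the parent judges tolerance and repeat use before exposure has ended.

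A reader might go further and conclude that tolerability will be overstated. The Protocol does not support that as a fact: it gives no rate of post-removal symptoms, so this is a risk of unknown size, with each missed child worth 3.1 percentage points. The Protocol sets no safety threshold that one or two missed events would cross.

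The conclusion assumes that the forms match their summary in Section 5 and that no other symptom record is kept. Severity is minor; it is worth acting on because the remedy is cheap and the lost data cannot be regained.

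**What to change.** Three changes to data collection in Section 5 and the forms:

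1. Extend the child's third question to cover feeling unwell *while wearing it or since taking it off*, and ask it last, after the pain score and the other two questions. Note the time since removal, so the window covered is known.
2. Move the parent's tolerance and repeat-use items until the headset is off, but before the child's questions are put, so that the parent's rating is not shaped by the child's answers.
3. Leave the parent's pain score and the item on whether the headset helped straight after the procedure, where recall is freshest.

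The cost is a few words on one form, two items moved on another and a few more minutes at the bedside, with no extra visit or participant. A limit remains: symptoms starting after the last question would still go unrecorded, and the report should say that observation ended there.

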7.2 Sampling

7.2.1 Size of sample

For this feasibility study, we aim to recruit 32 children during a 4 week period. Using the primary outcome acceptability of patient use, 32 children will enable us to identify our acceptability target of 75% of patients with 95% CI 56.6-88.5% (Clopper-Pearson exact). This number will also provide meaningful representation of a spread of gender, age groups, complexity of underlying illness, cultural and ethnic backgrounds to design future studies.

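### Parents and clinicians return their opinions of the headset by hand to the researcher who set it up, and no sealed or private return is described

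*Protocol*

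**What the plan says.** Protocol section 5 gives the researcher the initial setup of the headset and no further part in the procedure. Afterwards, parents and clinicians complete feedback forms. The parents' form covers perceived pain, acceptability, whether they would use the headset again, tolerance and whether it helped. The clinicians' form covers ease of use and whether the headset helped or prolonged the procedure. On return of the forms the text says: "Forms will be filled in by parents and clinicians themselves and then handed to the researcher". Pseudonymisation comes later in the sequence.

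For the child, the text reads: "Prior to application of VRH children will be asked to score their current pain score using the Wong Baker Faces Score (WBFS", and of that score, "This will be transcribed by the researcher". After the procedure: "Children will then have the VRH removed and be asked to score their current pain again using the WBFS". Acceptability to the child is handled separately: "Assessment of acceptability/feasibility for children will be based on 3" questions, namely liking, comfort and feeling unwell. The Protocol does not say who asks or records the second pain score or the three answers.

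Section 7.2.1 ties the sample size to the child's view ("Using the primary outcome acceptability of patient use") and states that "32 children will enable us to identify our acceptability target of 75% of patients with 95% CI 56.6-88.5% (Clopper-Pearson exact". Section 2 also asks whether parents and staff find the headset acceptable, and section 4.2 lists clinicians' feedback as an outcome.

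**The concern.** An opinion of a device is returned in person to the individual who brought it into use. Section 8.6 describes the research team as doctors of the same hospital. A parent of a current inpatient therefore gives the form to a hospital doctor, and a clinician gives it to a colleague. In that setting some respondents may answer more kindly than they feel.

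The study has one group, so there is no second set of answers in which a general tendency to please could be seen or allowed for. What is at stake is the parent and clinician feedback, which is meant to inform whether and how a randomised trial follows (section 4.1, objective 3).

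**Working it through.** **Step 1. Follow each answer to the result it feeds.**

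| Answer | How it is collected (section 5) | Result it feeds |
|---|---|---|
| Parent form | Self-completed, given by hand to the researcher | Parent-reported pain and acceptability |
| Clinician form | Self-completed, given by hand to the researcher | Clinician feedback (section 4.2, item 3) |
| Child's pain score before the headset | Transcribed by the researcher | Baseline of the pain comparison |
| Child's pain score after removal | Recorder not stated | Pain comparison |
| Child's three questions | Asker and recorder not stated | Primary outcome (section 7.2.1) |

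The quoted return route covers the first two rows only.

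**Step 2. Reproduce the Protocol's own figure.** Inputs from section 7.2.1: n = 32 and a target of 75%, so x = 0.75 × 32 = 24. The Clopper-Pearson limits are beta quantiles:

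- lower = Beta quantile 0.025 with parameters x = 24 and n − x + 1 = 9, which gives 0.566
- upper = Beta quantile 0.975 with parameters x + 1 = 25 and n − x = 8, which gives 0.885

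This matches the stated 56.6% to 88.5%. No stated figure is wrong. All 24 counted responses are children's, so no change to the adult forms alters x or the interval.

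**Step 3. What courtesy answers could do to an adult item.** The Protocol gives no bias size, so this is sensitivity only. Assume one parent form per child, n = 32, and a yes/no item. If k of the favourable answers are given out of courtesy, the observed share exceeds the true share by k/n:

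- k = 1: 1/32 = 3.1 percentage points
- k = 3: 3/32 = 9.4 points
- k = 5: 5/32 = 15.6 points

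The range of 1 to 5 is an assumption. The Protocol does not fix the number of clinician forms, and one clinician may treat several children, so no equivalent figure is given for them.

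**Step 4. What a sealed return can reach.** It bears on rows one and two. The last two rows need a separate provision, because the Protocol names no recorder there. The only recorder it names for any child response is the researcher, for the score taken before the headset goes on.

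**The case against.** The strongest case for leaving the text alone is that adults already fill in the forms themselves and that the researcher stays out of the procedure after setup. Both are partial safeguards. Handing a completed form to a researcher is ordinary practice in a small feasibility study, and nothing shows how much bias an envelope would remove. The remedy also has drawbacks. At n = 32 each lost answer costs about 3 percentage points of the sample, and a young child helped by a parent may be swayed by the parent instead. These points stand. They keep the matter minor but do not remove it, since a private return needs no extra staff and the text describes none.

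A reader might infer several stronger things that the Protocol does not support:

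- **That the forms are open or read on receipt.** The text says only that they are handed over.
- **That the researcher's transcription inflates acceptability.** The transcribed item is a pain score given before the headset is worn. It cannot carry courtesy about the headset.
- **That the adult forms inflate the 75% result.** That target rests on the child's three questions (step 2).
- **That the gain can be computed.** If true acceptability among children were 65%, the chance of 24 or more of 32 would be 0.16. If 10%, 20% or 30% of children who would say no said yes, it would be 0.28, 0.44 or 0.62. The arithmetic is sound, but the true rate, the bias and the pass mark are all assumed. Section 7.2.1 states a target and an interval without a pass rule. The figures concern children only and do not measure what the change would gain.

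**Conclusion.** The concern holds in a limited form. The Protocol fixes a return route that exposes parent and clinician opinions to courtesy bias in a single-group study. It also leaves unstated who obtains the child's answers on which the primary outcome rests.

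The size of any bias is unknown. The figure of 3.1 points per courtesy answer assumes one parent form for each of 32 children and says nothing about how many such answers there would be. The conclusion also takes the researcher who sets up the headset and the one who receives the forms to be the same person, which is the natural reading because section 5 uses the one term for both. The sample size calculation and its interval are unaffected. This is a worthwhile refinement, not a flaw that undermines the study.

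**What to change.** In section 5, replace the hand-over of the forms with wording such as: *each form carries only the study code and is sealed by the parent or clinician in an envelope, or put in a closed box, before return.*

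For the child, state how the answers after the procedure are obtained. Where the child is able, let the child mark the face and the three acceptability answers on a picture sheet rather than tell them to the person who set up the headset. The answer on feeling unwell should still be noted at the bedside, so that sealing does not hide it.

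The cost is envelopes or a box, a picture sheet and a few changed sentences, with no extra staff and no change to sample size. Completeness can no longer be checked on the spot, so a few items may be missed. Younger children may need a parent's help, and it would be useful to record on the sheet when help was given.
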